1.1 Inclusion Criteria for Research Subjects

1.1.1 Inclusion criteria:

- ✓ Age 60-80 years old, including 60 and 80 years old
- ✓ Living in the community
- ✓ Expected to live in their current place of residence for the next 12 months
- ✓ can walk 50 metres without the assistance of an assistive device

1.1.2 Exclusion criteria:

- ✗ Exclusion of study subjects with acute illnesses or acute stages of chronic diseases

1.1.3 Requirements for the proportion of recruited subjects

In order to increase the homogeneity of study subjects, study subjects can be recruited with reference to the following gender and age requirements:

① 20% male, 80% female; ② 30%-35% aged 60-65 years, ③ 30%-35% aged 66-70 years, ④ 30%-35% aged 71-75 years, ⑤ less than 10% aged 76-80 years.

(2) Sample size estimation

After scientific calculations, combined with the actual work, a total of 888 people are needed for this project, then each group needs a sample size of $n=111$, and a total of 37 people are recruited in each street (town). The sample size calculation process is as follows:

This study uses the dichotomous variable "whether a fall occurs" as the outcome indicator. According to the results of the occurrence of falls among the elderly in the community in Guangzhou City in 2023, the incidence of falls among the elderly in Baiyun District was 17%. After discussion with experts, it was concluded that a 35% reduction in the incidence of falls after the intervention was considered to be of public health significance. In this study, the test level was set at $\alpha=0.05$ and the test efficacy at 0.8 (i.e., $\beta=0.2$). The proposed factorial design for this study is based on the sample size formula (below) for factorial designs in which the outcome variable is a dichotomous variable, and the sample size required for each test condition can be obtained as:

$$n = \frac{(Z_{1-\alpha/2} + Z_{1-\beta})^2}{2^k [\arcsin(\sqrt{\frac{\rho+\rho\delta}{2}}) - \arcsin(\sqrt{\frac{\rho-\rho\delta}{2}})]^2} \approx 83$$

$$\rho=0.17, \delta=0.35, Z_{1-\alpha/2}=1.96, Z_{1-\beta}=0.84, k=3.$$

The total sample size required for the 8 test conditions was:

$$N_{\text{conditions}} = 83 \times 8 = 664$$

According to S. Bhasin, T.M et al, the design effect of whole cluster randomisation can be obtained by estimating $ICC = 0.0076$ and mean number of individuals in the cluster $m = 28$:

$$DE = 1 + (m-1) \times ICC = 1 + (28-1) \times 0.0076 = 1.2052$$

The sample size was set to be the same for the eight test conditions, and the total sample size required for the study was:

$$N = N_{\text{conditions}} \times DE \div (1 - 10\%) \approx 888$$

The required sample size for each test condition was then 111 cases;

Each of the 24 streets recruited 37 study participants.

(3) Intervention groups

The study subjects were grouped in a completely randomised manner, with a statistician independent of the research team using a computer to generate random numbers, and equal proportions of the study subjects recruited from the 24 streets (towns) were allocated to the 8 experimental condition groups, so that each experimental condition contained all the study subjects from 3 streets (towns). After grouping was completed, a database of basic information about the study participants was created, as shown in Table 1. This study was blinded only to the data collectors and data analysers.

Table 1 Subgroups of the Community Falls Prevention for Older People Pilot Project

groups	Fall Prevention Education Course	Development of personal exercise skills	Environmental assessment
Group 1	Yes	Yes	Yes
Group 2	Yes	Yes	No
Group 3	Yes	No	Yes
Group 4	Yes	No	No
Group 5	No	No	No
Group 6	No	Yes	Yes
Group 7	No	Yes	No
Group 8	No	No	Yes

IV. Intervention Strategies

(1) Strategy 1: Falls prevention education programme

To organise the research subjects in the intervention group to set up a fall prevention health education activity group, in which the project team will disseminate knowledge and concepts of fall prevention through lectures, discussions, questions and answers, and sharing, so as to enhance the knowledge base required by the research subjects to prevent falls and to cultivate the relevant concepts.

(2) Strategy 2: Developing personal exercise skills

Through lectures, demonstrations, on-site exercises and practices, the project team taught the intervention group participants to improve their balance function, lower limb muscle strength, endurance exercise and other fall prevention exercise skills, and to use fall prevention aids through group activities.

(3) Strategy 3: Environmental Assessment

Through the staff's home assessment and guidance, the project team instructed the study participants to assess the risk factors of fall-related home environment and made suggestions for modification.

V. Main intervention activities

(1) Strategy 1: Fall prevention education programme:

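### The 80% power stated for a 35% reduction from 17% rests on rates of 11.475% v 5.525%; from explicit marginal rates, 888 participants give 60%, or less if the other components also work and effects multiply

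*Combined protocol and SAP*

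**What the plan says.** Section III (2), Sample size estimation, uses occurrence of a fall as a binary outcome. Its only event-rate input is a district survey result: "the incidence of falls among the elderly in Baiyun District was 17" per cent. The target is that "a 35% reduction in the incidence of falls after the intervention was considered to be of public health significance". It does not say whether the 35% belongs to one component or to the whole package. Alpha is 0.05 with z = 1.96, and power is 0.8 with z = 0.84.

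The arcsine formula for a factorial with k = 3 factors gives about 83 per condition, or 664 over eight conditions. A design effect of 1.2052 and 10% loss bring this to 888, or 111 per condition.

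Section III (3) sets out the eight groups under "Table 1 Subgroups of the Community Falls Prevention for Older People Pilot Project". This is a complete 2x2x2 factorial, and only Group 5 receives no component. Neither section states what the other components are assumed to do when one component is tested.

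**The concern.** In a factorial, each component is tested by comparing four Yes groups with four No groups. The rates that matter are averages over those four groups. Table 1 shows that the No groups are mostly treated:

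- Education: No groups are 5, 6, 7 and 8; groups 6, 7 and 8 receive something else.
- Exercise: No groups are 3, 4, 5 and 8; groups 3, 4 and 8 receive something else.
- Environment: No groups are 2, 4, 5 and 7; groups 2, 4 and 7 receive something else.

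If the other components work, the No-level rate lies below 17%, and the absolute difference from a given relative reduction shrinks with it. The plan expects components to work: section I reports 4.35% v 24% falls in the first round of the earlier multicomponent project. The sample size section contains no step that turns 17% and 35% into marginal rates. The 80% figure is the trial's only statement of how reliably it can detect a useful component, and the trial exists to choose among components.

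**Working it through.** **Inputs from section III (2).** Rate 0.17; reduction 0.35; z values 1.96 and 0.84 (sum 2.80); k = 3; design effect 1.2052; loss 10%; N = 888. The design effect is taken as stated.

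**1. The plan's own figure.** The formula enters
- (0.17 + 0.17 x 0.35)/2 = 0.11475
- (0.17 - 0.17 x 0.35)/2 = 0.05525

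The gap is 0.0595 and the relative reduction is 0.0595/0.11475 = 52%. The arcsine difference is 0.3456 - 0.2373 = 0.1083, so n = 2.80²/(8 x 0.1083²) = 83.5 per condition. Then 83 x 8 = 664, and 664 x 1.2052/0.9 = 889 (stated 888). The stated figures therefore follow from the formula as printed.

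**2. The stated inputs in the same formula.** With 17% v 0.65 x 17% = 11.05%, the arcsine difference is 0.4250 - 0.3389 = 0.0861. This gives n = 2.80²/(8 x 0.0861²) = 132 per condition, not 83.

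**3. Power at the planned size.** Effective N = 888 x 0.9/1.2052 = 663. Power = Φ(√663 x arcsine difference - 1.96).
- Printed rates: Φ(2.79 - 1.96) = 80%.
- 17% v 11.05%: Φ(2.22 - 1.96) = 60%.

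**4. Marginal rates, ratio scale.** Let each of the other two components cut falls by r, with effects multiplying. Each is present in half the groups at either level, so the No rate is 0.17 x (1 - r/2)² and the Yes rate is 0.65 times that. The values of r are assumptions; the documents give none. The last column is the relative reduction at which √663 x arcsine difference = 2.80.

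| r | No | Yes | Power for 35% | Detectable with 80% power |
|---|---|---|---|---|
| 0 | 17.0% | 11.05% | 60% | 43% |
| 10% | 15.3% | 10.0% | 55% | 45% |
| 20% | 13.8% | 9.0% | 50% | 48% |
| 35% | 11.6% | 7.5% | 43% | 52% |

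**5. Marginal rates, additive scale.** Hold the tested component's effect at 5.95 points (17% x 35%) and let each other component remove a fraction s of 17%. The No rate is 0.17 x (1 - s), and the all-Yes cell is 0.17 - 0.0595 - 2 x 0.17s.

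| s | No | Yes | Power | All-Yes cell |
|---|---|---|---|---|
| 10% | 15.3% | 9.35% | 65% | 7.65% |
| 20% | 13.6% | 7.65% | 71% | 4.25% |
| 32.5% | 11.475% | 5.525% | 80% | 0% |
| 35% | 11.05% | 5.10% | 82% | -0.85% |

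On this scale the printed rates appear only at s = 32.5%, where nobody receiving all three components would fall.

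**The case against.** A reader might infer that the plan sets the No level at 17% and that this is what costs the power. The formula does not support that. It never enters 17% at either level, and doing so would have given 132 per condition. The drop from 80% to 60% comes from the halving inside the arcsine terms. Active co-components account only for the further 5 to 17 points, and for none if they are inert.

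The 11.475% that the formula uses is also close to the 11.57% No rate that results when every component cuts falls by 35% on the ratio scale. That is true, but the match is at one level only. A 35% reduction from 11.57% gives 7.52%, not 5.525%.

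The strongest objection concerns scale. The formula preserves an absolute gap of 5.95 points, and if that gap is held fixed, active co-components raise power rather than lower it. This stands: the documents name no scale, so a loss from co-components cannot be stated unconditionally. It does not rescue the 80%, because the additive cases with a plausible all-Yes rate still fall short.

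Reading the 35% as per component is likewise an assumption. Reading it as the effect of the full package would not help. Split equally on the ratio scale, each component would cut falls by 1 - 0.65^(1/3) = 13.4%; the marginal rates would be 14.8% v 12.8% and power 11%.

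A reader might also infer that a non-significant component will be dropped. The documents contain no such rule: section II bases the choice on quantitative comparison together with economic evaluation.

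**Conclusion.** The concern holds as a conditional range. The 80% is correct for 11.475% v 5.525%, a 52% relative reduction, and not for the 35% reduction from 17% that the text describes. For a 35% relative reduction from one component, 888 participants give 60% power if the other components are inert. On the ratio scale this falls to 55%, 50% or 43% if each of the others cuts falls by 10%, 20% or 35%. The smallest reduction detectable with 80% power rises from about 43% to about 52% between the inert case and the 35% case, and both exceed the plan's own 35%. On the additive scale with a fixed 5.95-point gap, power is 65% or 71% for co-components removing 10% or 20% of 17%. It reaches about 80% only when the all-Yes cell is at or below about zero.

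These figures assume that 35% applies to each component, that the stated design effect and 10% loss are right, and that the effects do not interact on the chosen scale.

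**What to change.** In section III (2):

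- State whether the 35% is the effect of a single component or of the package, and whether effects are taken to multiply or add.
- Compute each main effect from explicit marginal rates over the four Yes and four No groups of Table 1. On the ratio scale these are 0.17 x (1 - r/2)² for No and 0.65 times that for Yes, with r stated as an assumption.
- Replace the 80% claim with the power, or the smallest detectable reduction, that 888 participants give over the assumed range of r, for example 0 to 35%.

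The cost is one recalculation and a revised paragraph. Enrolment need not change.

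### The sample-size formula enters fall rates of 11.5% and 5.5% instead of the stated 17% and 11.05%, so 888 participants give about 60% power for a 35% reduction, not 80%

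*Combined protocol and SAP*

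**What the plan says.** Section III (2), Sample size estimation, sizes the trial on a binary outcome: "This study uses the dichotomous variable 'whether a fall occurs' as the outcome indicator". It reports that "the incidence of falls among the elderly in Baiyun District was 17" per cent in 2023. For the effect, "it was concluded that a 35% reduction in the incidence of falls after the intervention was considered to be of public health significance". The test is two-sided at 0.05 (z = 1.96), with "the test efficacy at 0.8" (z = 0.84).

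The formula is an arcsine formula for a factorial with k = 3 components, ρ = 0.17 and δ = 0.35. Its two proportions are (ρ + ρδ)/2 and (ρ − ρδ)/2. It gives about 83 per condition and 664 over eight conditions. A design effect of 1.2052 (ICC 0.0076, 28 per cluster) and 10% loss bring this to 888. On allocation: "The sample size was set to be the same for the eight test conditions", which makes 111 per condition and 37 in each of 24 streets.

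**The concern.** The two proportions in the formula should be the fall rates without and with a component. On the stated inputs these are 17% and 11.05%. The formula uses 11.475% and 5.525%, which appear nowhere in the text: it takes half of ρ(1 + δ) = 22.95% and half of ρ(1 − δ) = 11.05%. The absolute gap of 5.95 points is right, but it is centred on 8.5% instead of about 14%. A binomial variance is smaller there, so the required sample size comes out too small.

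The trial exists to screen components (section II, specific objective 1.1). The Background itself warns that if component effects are unknown, the one dropped may be the one that works. The plan accepts a 20% chance of missing a component that meets the target. If the real chance is about 40%, a reader told that power was 80% will give too much weight to a null result.

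**Working it through.** **Inputs, all from section III (2):** ρ = 0.17; δ = 0.35; z values 1.96 and 0.84, so (2.80)² = 7.84; k = 3, so 2^k = 8; design effect 1.2052; loss 10%; N = 888.

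**Formula:** n per condition = 7.84 / (8 d²), with d = asin√p1 − asin√p2. Over eight conditions this is N = 7.84/d², the usual arcsine two-proportion total for four conditions against four. The divisor 2^k is therefore correct for a main effect.

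**1. The plan's own figure**
- p1 = 0.2295/2 = 0.11475; p2 = 0.1105/2 = 0.05525.
- d = 0.34559 − 0.23727 = 0.10831.
- n = 7.84 / (8 × 0.011732) = 83.5, printed as 83.
- 83 × 8 = 664; 664 × 1.2052 / 0.9 = 889.2, printed as 888.
- Implied relative reduction: 1 − 0.05525/0.11475 = 52%.

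Apart from rounding, the calculation follows the printed formula, so the printed proportions are the ones that were used.

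**2. The stated target**
- p1 = 0.17; p2 = 0.17 × 0.65 = 0.1105.
- d = 0.42499 − 0.33886 = 0.08613.
- n = 7.84 / (8 × 0.0074176) = 132.1, so 133 per condition.
- Total: 133 × 8 × 1.2052 / 0.9 ≈ 1,425.

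**3. Power at N = 888**
- Effective N = 888 × 0.9 / 1.2052 = 663.1, or 331.6 per level of a component.
- Power = Φ(√663.1 × 0.08613 − 1.96) = Φ(0.258) = 60.2%.
- Cross-check with the pooled two-proportion formula, 331.6 per level: 59.8%.

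**4. Detectable effect at 80% power**
- Required d = 2.80/√663.1 = 0.10873. From 17%, this means a rate of about 9.67%, a relative reduction of about 43%.

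**5. Other readings of ρ and δ**

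| Reading | Rates | n per condition | Power at 888 |
|---|---|---|---|
| As stated | 17% vs 11.05% | 132.1 | 60% |
| 17% as the mean, gap ρδ | 19.975% vs 14.025% | 155.1 | 53% |
| 17% as the mean, true 35% relative reduction | 20.6% vs 13.4% | 105.2 | 70% |
| ρ(1 ± δ) without halving | 22.95% vs 11.05% | 37.9 | 99% |

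None gives 83. The last row is a 52% reduction, not 35%.

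**6. Easier assumptions at 17% vs 11.05%**
- One-sided test at 0.05: 72%.
- No design effect and no loss: 73%.

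Neither reaches 80%.

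**7. Less favourable assumptions**
- Cluster size 37, as the plan recruits, instead of 28: design effect 1 + 36 × 0.0076 = 1.2736, effective N = 627.5, power about 58%.
- Assumption not in the plan: other components also cut falls by 35%, acting multiplicatively. With one other active, the averaged rates are 14.03% vs 9.12% and power is 51%. With both active, they are 11.57% vs 7.52% and power is 43%.

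**The case against.** The strongest objection is that the shortfall depends on the 17% baseline. The Background reports 24% falls in the control group of the programme's first round. At 24% vs 15.6%, with the same design effect, loss and N, d = 0.10594 and power is Φ(25.751 × 0.10594 − 1.96), about 78%. The trial might therefore be nearly adequate in practice. But the plan commits to 17% for the district and carries that value into the formula, so its power claim has to hold at 17%.

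Second, ρ is never defined in words, and reading it as the average of the two rates narrows the gap to 70% power. That is true, but it still gives 105 per condition, not 83.

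Third, 60% and 1,425 both keep 28 per cluster, although the plan recruits 37 per street. This stands, and it works against the plan. Power falls to about 58%. If the streets stay at 24, a larger total also enlarges the clusters: solving 0.9N = 1,064 × [1 + (0.9N/24 − 1) × 0.0076] gives about 1,770, so 1,425 is a lower figure.

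Fourth, the 60% presumes a pooled comparison of four conditions with four. Section VII (2) names only t-tests and chi-square tests between groups and sets out no main-effect model. That is a fair condition on the figure, but the plan's own sample-size formula makes the same presumption.

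Finally, no rule says that a component is dropped when its test is non-significant, and cost-effectiveness also enters the choice. Wrongful removal is therefore a risk, not a certainty.

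**Conclusion.** The point holds. The power claim contradicts the inputs printed beside it. At the plan's own 17% incidence, 35% reduction, two-sided 0.05, design effect of 1.2052, 10% loss and N = 888, the main effect of one component has about 60% power when the other components have no effect. The chance of missing a component that meets the target is about 40%, twice what the plan accepts. At 80% power the design detects a relative reduction of about 43%. The result does not depend on the choice between arcsine and pooled formulas, and no coherent reading of the stated inputs recovers 83 per condition. A higher true fall rate would raise power; the planned cluster size of 37, or other active components, would lower it. This must be corrected, because it concerns the outcome on which the trial is sized.

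**What to change.** In section III (2):

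- Replace the two arcsine arguments with ρ = 0.17 and ρ(1 − δ) = 0.1105, and define ρ in words as the fall rate without the component.
- Keep N = 888 and remove the claim of 80% power for a 35% reduction. State instead either about 60% power for a 35% relative reduction, or 80% power for about a 43% relative reduction.
- Say that this applies to the main effect of one component, four conditions against four, and give the assumption made about the other components.
- Give the cluster size behind the figure. With 37 per street, power for a 35% reduction is about 58%. The required d is 2.80/√627.5 = 0.1118, a detectable reduction of about 44%.

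In section VII (2), add that each component's effect is reported with its confidence interval, and that a non-significant component is not called ineffective while the interval still includes a 35% reduction.

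The cost is rewording and a less favourable power statement. There are no extra participants and no change to the design or the interventions.

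### The design effect assumes 28 people per cluster, but the plan recruits 37 per street (about 33 analysed); if whole streets are allocated it is about 1.25, not 1.2052

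*Combined protocol and SAP*

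**What the plan says.** Section III (2), Sample size estimation, first obtains 83 people per condition, or 664 over eight conditions. It then says that "the design effect of whole cluster randomisation can be obtained by estimating" an ICC of 0.0076 and a "mean number of individuals in the cluster $m = 28". The resulting design effect of 1.2052 multiplies 664, and the product is divided by 0.9 for 10% loss, giving about 888. The section ends by fixing the layout: "Each of the 24 streets recruited 37 study participants".

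On the unit of allocation, section III (3), Intervention groups, points both ways. It begins "The study subjects were grouped in a completely randomised manner" and adds that "equal proportions of the study subjects recruited from the 24 streets (towns) were allocated to the 8 experimental condition groups", then concludes "so that each experimental condition contained all the study subjects from 3 streets (towns". Section III (1) speaks of eligible people being assigned at random to the groups. Section VI (2) 2.3.3 ties communities to numbered groups but does not name the street as the unit.

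**The concern.** An ICC may be borrowed from another study. The number of people per cluster is set by this trial's own layout. If the street is the allocated cluster, the layout gives 37 recruited and about 33 analysed, and no section describes a cluster of 28. A cluster size that is too small gives a design effect that is too small, so the calculation credits 888 recruits with more information than they carry. There is no slack to absorb this, because the printed inputs already give 889.2 against the 888 adopted.

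**Working it through.** **Inputs, all from section III (2):** 664 before inflation; ICC 0.0076; m = 28; loss 10%; 24 streets; 37 recruits per street; Z values 1.96 and 0.84 (sum 2.80).

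**1. The plan's own figures.**
- Printed formula: n = 83.54 per condition, against 83 printed. Unrounded total: 8 × 83.54 = 668.3, against 664.
- Design effect: 1 + 27 × 0.0076 = 1.2052, as printed.
- Total: 664 × 1.2052 / 0.9 = 889.2, against 888 = 24 × 37. The gap is rounding, and I make nothing of it.

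**2. The matching cluster size.** The plan applies the design effect before dividing by 0.9, so the design effect belongs to the analysed sample. Analysed per street: 37 × 0.9 = 33.3. Analysed in total: 24 × 33.3 = 799.2.

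**3. Design effect and effective sample at 888 recruited.**

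| m | Design effect | Effective sample |
|---|---|---|
| 28 (printed) | 1.2052 | 799.2 / 1.2052 = 663.1 |
| 33.3 (analysed) | 1 + 32.3 × 0.0076 = 1.2455 | 799.2 / 1.2455 = 641.7 |

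**4. Total the plan's method would require.**
- With m fixed at 33.3: 664 × 1.2455 / 0.9 = 918.9.
- Solving street size and total together, because more recruits also enlarge the streets: analysed N = 664 × (1 − 0.0076) / (1 − 664 × 0.0076 / 24) = 834.4, and 834.4 / 0.9 = 927.1.

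**5. Power, changing only m.**
- Taking 664 as the 80% point: Φ(2.80 × √(n_eff / 664) − 1.96) = 79.9% at m = 28 and 78.6% at m = 33.3.
- Taking the unrounded 668.3: 79.65% and 78.34%.

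Both give a drop of about 1.3 points. These figures isolate m and nothing else. The printed formula halves its rates, so it compares 0.17 × 1.35 / 2 = 11.475% with 0.17 × 0.65 / 2 = 5.525%.

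**6. The same step on the stated effect.** The text says that "the incidence of falls among the elderly in Baiyun District was 17" per cent and that "a 35% reduction in the incidence of falls after the intervention was considered to be of public health significance". That is 17% against 17% × 0.65 = 11.05%. The arcsine difference is asin√0.17 − asin√0.1105 = 0.0861, and Φ(0.0861 × √n_eff − 1.96) gives 60.2% at m = 28 and 58.8% at m = 33.3. The cost of m is again about 1.4 points; the fall from 80% to about 60% comes from the rates.

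**7. What would offset the error.**
- An ICC of 0.2052 / 32.3 = 0.00635 in place of 0.0076.
- A loss of 6.0% in place of 10%: 888 × 0.94 = 834.7 analysed, 34.78 per street, design effect 1 + 33.78 × 0.0076 = 1.2567, effective sample about 664.

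**The case against.** **The premise is unsettled.** If individuals are allocated, a street design effect does not apply in this form, and m = 28 cannot be called right or wrong until the unit is known. This stands as a condition on the finding. The street reading nevertheless has real support: the calculation itself invokes whole-cluster randomisation, section III (3) puts three streets in each condition, and 3 × 37 = 111 is the printed group size. On the other reading the cluster line needs revision or justification, so the text needs attention either way. Activity groups do not supply a cluster of 28, since section V (1.3 and 2.3) sets them at 12 and in principle no more than 15.

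**The figure may have an innocent origin.** 664 / 24 = 27.7, which rounds to 28, so m may be the street size before inflation, never updated. The sentence can also be read as taking 28 from the cited study, which cannot be checked here. Either is plausible and neither is stated. Both explain how 28 could arise; neither makes it the number per street in this trial.

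**The shortfall depends on losing the full 10%.** If all 37 per street were analysed, the design effect would be 1 + 36 × 0.0076 = 1.2736, the effective sample 888 / 1.2736 = 697, and power about 82% on the plan's basis. That is correct arithmetic, but 10% is the plan's own assumption. Section VII (2) specifies intention-to-treat without saying how missing outcomes are handled.

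**The effect is small, and nothing is added up wrongly.** Both are true. The sum is right; the fault lies in an input. A modest change in the ICC would cancel it, which is why the point is minor.

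**Conclusion.** The point holds, conditionally, and is minor. If whole streets are allocated, the printed design effect does not describe the trial: it is 1.2455 on the analysed street size, not 1.2052. The effective sample at 888 is about 642 against the 664 required, and power drops by about 1.3 points. This assumes the plan's ICC of 0.0076, its 10% loss spread evenly over streets, and equal street sizes. The error runs in one direction on this reading, but it is a small part of the distance between the trial's real power and 80%.

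**What to change.** Reconcile sections III (1), III (2) and III (3) so that they name one unit of allocation. Which unit is used is for the sponsor to state.

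- **If the street:** replace m = 28 with the expected number analysed per street (33.3, design effect 1.2455) and restate the power that 888 delivers.
- **If the individual:** revise the cluster-randomisation line and justify any design effect that is kept.

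Make this part of a single recalculation that also uses the stated rates of 17% and 11.05%. A figure of about 78% on the printed formula's halved rates should not be presented as the trial's power.

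The cost is a revision of the sample-size and allocation text, with no extra recruitment. The downside is that the restated power will fall below 80%. On the street reading it is about 59% with the stated rates, and m accounts for only 1.3 to 1.4 points of the shortfall.
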